#### **Ablation Zone Examples**

The ablation zone results examples contained in *Table 1* were developed using the ablation catheter kit in an in vivo porcine lung. The table includes the ablation diameter (A), height (B), and distance from the tip (C) versus time (MM:SS) for three power levels (45 watts, 75 watts, and 100 watts).

The circular areas in *Figure 4* represent the zone of tissue coagulation created around the ablation catheter radiating section. The shape and size of ablation zones may vary in clinical settings.

		45 W			75 W				
A	MM:SS	В	C	MM:SS	В	C	MM:SS	В	C
1.6 cm	2:00	2.8 cm	0.6 cm						
1.9 cm	3:00	3.0 cm	0.7 cm	2:00	3.1 cm	0.8 cm			
2.2 cm	4:30	3.3 cm	0.8 cm	2:30	3.3 cm	0.9 cm			
2.5 cm	7:30	3.5 cm	0.9 cm	3:30	3.6 cm	0.9 cm	2:30	3.3 cm	0.7 cm
2.7 cm	10:00	3.6 cm	1.0 cm	4:30	3.8 cm	1.0 cm	3:00	3.5 cm	0.8 cm
2.9 cm				5:30	3.9 cm	1.1 cm	4:00	3.7 cm	0.8 cm
3.1 cm				7:00	4.0 cm	1.1 cm	5:00	3.9 cm	0.9 cm
3.3 cm				9:00	4.1 cm	1.1 cm	7:00	4.0 cm	1.0 cm
3.4 cm				10:00	4.2 cm	1.1 cm	8:30	4.1 cm	1.0 cm
3.5 cm							10:00	4.2 cm	1.0 cm

**Table 1** *In Vivo Porcine Lung* 

[figure not shown]

Figure 4

Do not esterilize

Not made with natural rubber latex

Consult instructions for use

Document No. DLB00794-01 Rev. A Part No. PLB00555-01 Rev. A

COVIDIEN, COVIDIEN with logo, and Covidien logo and Positive Results for Life are U.S. and internationally registered trademarks of Covidien AG. Other brands are trademarks of a Covidien company, ™\* brands are trademarks of their respective owner.

© 2014 Covidien.

Covidien Ilc, [name].

[figure not shown]
**ECREP** Covidien Ireland Limited [name].

Made in USA. Printed in USA.

www.covidien.com

REV 2016-06

[figure not shown]
Subject #
-----------

#### **Bronchoscopic Ablation Patient Pain and Satisfaction Survey**

As a participant in the NAVABLATE study, you are being asked to complete this survey. Please take a few minutes to complete the form. The information you provide will be used to evaluate patients' satisfaction with the Bronchoscopic Ablation procedure.

Date Survey Completed:

# UNIVERSAL PAIN ASSESSMENT TOOL

What level of pain or discomfort did you experience because of the Bronchoscopic Ablation procedure:	Using the scale above as a guide, please circle the number that best fits your answer:				е						
Immediately after the Bronchoscopic Ablation procedure?	0	1	2	3	4	5	6	7	8	9	10
One week after the Bronchoscopic Ablation procedure?		1	2	3	4	5	6	7	8	9	10
One month after the Bronchoscopic Ablation procedure?	0	1	2	3	4	5	6	7	8	9	10

Grade	Degree of breathlessness related to activities (MRC Breathlessness Scale)*							
1	Not troubled by breathlessness except on strenuous exercise							
2	Short of breath when hurrying on the level or walking	up a sligh	t hill					
3	Walks slower than most people on the level, stops after 1.5 kilometers or so, or stops after 15 minutes walking at own pace							
4	Stops for breath after walking about 100 meters or after a few minutes on level ground							
5	Too breathless to leave the house, or breathless whe	n undress	ing					
	evel of breathlessness did you experience because Bronchoscopic Ablation procedure:		he scale a ne numbe :					
	Immediately after the Bronchoscopic Ablation procedure?	1	2	3	4	5		
	One week after the Bronchoscopic Ablation procedure?	1	2	3	4	5		
	One month after the Bronchoscopic Ablation procedure?	1	2	3	4	5		

	Please circle the number that best fits your answer									
	Extremely Unlikely	Unlikely	Neutral	Likely	Extremely Likely					
How likely would you be willing to have an Bronchoscopic Ablation procedure performed again if necessary?	1	2	3	4	5					
How likely would you recommend the Bronchoscopic Ablation procedure to family and friends if necessary?	1	2	3	4	5					

	Please circle the number that best fits your answer					
	Totally	Dissatisfied	Neutral	Satisfied	Extremely	
	Dissatisfied				Satisfied	
Overall, how satisfied were you	_	_		_	_	
with the Bronchoscopic Ablation	1	2	3	4	5	
procedure?						

Printed name of person completing this worksheet:				
Signature:	Date:			

\* Used with the permission of the Medical Research Council and adapted to include metric distance units.

## **Health Questionnaire**

**English version for the UK** 

(Validated for Ireland)

By placing a tick in one box in each group below, please indicate which statements best describe your own health state today.

Mobility	
I have no problems in walking about	
I have some problems in walking about	
I am confined to bed	
Self-Care	
I have no problems with self-care	
I have some problems washing or dressing myself	
I am unable to wash or dress myself	
Usual Activities (e.g. work, study, housework, family or leisure activities)	
I have no problems with performing my usual activities	
I have some problems with performing my usual activities	
I am unable to perform my usual activities	
Pain / Discomfort	
I have no pain or discomfort	
I have moderate pain or discomfort	
I have extreme pain or discomfort	
Anxiety / Depression	
I am not anxious or depressed	
I am moderately anxious or depressed	
I am extremely anxious or depressed	

# Best imaginable health state

To help people say how good or bad a health state is, we have drawn a scale (rather like a thermometer) on which the best state you can imagine is marked 100 and the worst state you can imagine is marked 0.

We would like you to indicate on this scale how good or bad your own health is today, in your opinion. Please do

We would like you to indicate on this scale how good or bad your own health is today, in your opinion. Please do this by drawing a line from the box below to whichever point on the scale indicates how good or bad your health state is today.

Your own health state today

Worst imaginable health state

## **Common Terminology Criteria for Adverse Events (CTCAE)**

A set of criteria for the standardized classification of adverse effects of drugs used in cancer therapy.

The CTCAE system is a product of the US National Cancer Institute Cancer Therapy Evaluation

Program. This protocol will use Version 5.0 (published 27-NOV-2017), available at

<a href="https://ctep.cancer.gov/protocolDevelopment/electronic\_applications/ctc.htm#ctc\_50https://ctep.cancer.gov/protocolDevelopment/electronic\_applications/ctc.htm#ctc\_50https://ctep.cancer.gov/protocolDevelopment/electronic\_applications/ctc.htm#ctc\_50https://ctep.cancer.gov/protocolDevelopment/electronic\_applications/ctc.htm#ctc\_50https://ctep.cancer.gov/protocolDevelopment/electronic\_applications/ctc.htm#ctc\_50https://ctep.cancer.gov/protocolDevelopment/electronic\_applications/ctc.htm#ctc\_50https://ctep.cancer.gov/protocolDevelopment/electronic\_applications/ctc.htm#ctc\_50https://ctep.cancer.gov/protocolDevelopment/electronic\_applications/ctc.htm#ctc\_50https://ctep.cancer.gov/protocolDevelopment/electronic\_applications/ctc.htm#ctc\_50https://ctep.cancer.gov/protocolDevelopment/electronic\_applications/ctc.htm#ctc\_50https://ctep.cancer.gov/protocolDevelopment/electronic\_applications/ctc.htm#ctc\_50https://ctep.cancer.gov/protocolDevelopment/electronic\_applications/ctc.htm#ctc\_50https://ctep.cancer.gov/protocolDevelopment/electronic\_applications/ctc.htm#ctc\_50https://ctep.cancer.gov/protocolDevelopment/electronic\_applications/ctc.htm#ctc\_50https://ctep.cancer.gov/protocolDevelopment/electronic\_applications/ctc.htm#ctc\_50https://ctep.cancer.gov/protocolDevelopment/electronic\_applications/ctc.htm#ctc\_50https://ctep.cancer.gov/protocolDevelopment/electronic\_applications/ctc.htm#ctc\_50https://ctep.cancer.gov/protocolDevelopment/electronic\_applications/ctc.htm#ctc\_50https://ctep.cancer.gov/protocolDevelopment/electronic\_applications/ctc.htm#ctc\_50https://ctep.cancer.gov/protocolDevelopment/electronic\_applications/ctc.htm#ctc\_50https://ctep.cancer.gov/protocolDevelopment/electronic\_applications/ctc.htm#ctc\_50https://ctep.cancer.gov/protocol

## **Instrumental Activities of Daily Living**

For the purpose of defining CTCAE grade, instrumental activities of daily living (ADL) refers to preparing meals, shopping for groceries or clothes, using the telephone, managing money, etc.

## **Self-Care Activities of Daily Living**

For the purpose of defining CTCAE grade, self-care activities of daily living (ADL) refer to bathing, dressing and undressing, feeding self, using the toilet, taking medications, and not bedridden.

## **Adverse Event and Device Deficiency Definitions**

## **Adverse Event (AE)**

- An Adverse Event (AE) is any untoward medical occurrence, unintended disease or injury, or untoward clinical signs (including abnormal laboratory findings) in subjects, users or other persons, whether or not related to the investigational medical device.\*
- \*For the purposes of this clinical study, AE definitions will be ISO 14155:2011 compliant with the following exception: only those adverse events that are related to the Emprint™ Ablation Catheter Kit with Thermosphere™ Technology, accessory devices, or study procedures will be captured and reported.
- NOTE 1: This definition includes events related to the investigational medical device or the comparator.
- NOTE 2: This definition includes events related to the procedures involved.
- NOTE 3: For users or other persons, this definition is restricted to events related to investigational medical devices.

## **Serious Adverse Event (SAE)**

For the purposes of this study, a Serious Adverse Event\* is an adverse event that has

1. Led to death,

Medtronic Confidential Version: 2.0, 24/Sep/2019 Page 2 of 11

- 2. Led to serious deterioration in the health of the subject, that either resulted in
  - a. A life-threatening illness or injury, or
  - b. A permanent impairment of a body structure or a body function, or
  - c. In-patient or prolonged hospitalization, or
  - d. Medical or surgical intervention to prevent life-threatening illness or injury or permanent impairment to a body structure or a body function.
- 3. led to fetal distress, fetal death or a congenital abnormality or birth defect
- NOTE 1: This includes device deficiencies that might have led to a serious adverse event if a) suitable action had not been taken or b) intervention had not been made or c) if circumstances had been less fortunate. These are handled under the SAE reporting system.
- NOTE 2: Planned hospitalization for a pre-existing condition, or a procedure required by the clinical investigational plan, without serious deterioration in health, is not considered a serious adverse event.
- \*For the purposes of this clinical study, SAE definitions will be ISO 14155:2011 compliant with the following exception: only those SAEs that are related to the Emprint™ Ablation Catheter Kit with Thermosphere™ Technology, accessory devices, or study procedures will be captured and reported.

#### **Adverse Device Effect (ADE)**

- An Adverse Device Effect (ADE) is an adverse event related to the use of the investigational medical device (the Emprint™ Ablation Catheter Kit with Thermosphere™ Technology).
- NOTE 1: This definition includes adverse events resulting from insufficient or inadequate instructions for use, deployment, implantation, installation, or operation, or any malfunction of the investigational medical device.
- NOTE 2: This definition includes any event resulting from use error or from intentional misuse of the investigational medical device.

#### Serious Adverse Device Effect (SADE)

A Serious Adverse Device Effect (SADE) is an adverse device effect that has resulted in any of the consequences characteristic of a serious adverse event.

#### **Unanticipated Serious Adverse Device Effect (USADE)**

An Unanticipated Serious Adverse Device Effect (USADE) is defined as serious adverse device effect which by its nature, incidence, severity or outcome has not been identified in the current version of the Risk Management Report.

#### **Device Deficiency**

Inadequacy of a medical device with respect to its identity, quality, durability, reliability, safety or performance.

Note: Device deficiencies include malfunctions, use errors, and inadequate labelling.

Medtronic Confidential Version: 2.0, 24/Sep/2019 Page **3** of **11** 

## **Adverse Event Relationship and Outcome Classifications**

#### **Adverse Event Relationship Classification**

Causality assessments define the relationship between the use of the medical device (including the procedure) and the occurrence of each adverse event. During causality assessment activity, clinical judgment shall be used and the relevant documents, such as the MDR Reportable Event Trend & Risk Analysis Report shall be consulted, as all the foreseeable serious adverse events and the potential risks are listed and assessed there. The presence of confounding factors, such as concomitant medication/treatment, the natural history of the underlying disease, other concurrent illness or risk factors shall also be considered.

Each AE and SAE will be classified according to five different levels of causality. The following definitions will be used to assess the relationship of the adverse event to the investigational medical device (the Emprint™ Ablation Catheter Kit with Thermosphere™ Technology), accessory devices, or procedures:

- *Not related*: Relationship to the device or procedures can be excluded when:
  - the event is not a known side effect of the product category the device belongs to or of similar devices and procedures
  - the event has no temporal relationship with the use of the investigational device or the procedures;
  - o the serious event does not follow a known response pattern to the medical device (if the response pattern is previously known) and is biologically implausible;
  - the discontinuation of medical device application or the reduction of the level of activation/exposure - when clinically feasible – and reintroduction of its use (or increase of the level of activation/exposure), do not impact on the serious event;
  - the event involves a body-site or an organ not expected to be affected by the device or procedure;
  - the serious event can be attributed to another cause (e.g. an underlying or concurrent illness/ clinical condition, an effect of another device, drug, treatment or other risk factors);
  - the event does not depend on a false result given by the investigational device used for diagnosis, when applicable;
  - o harms to the subject are not clearly due to use error;
  - o In order to establish the non-relatedness, not all the criteria listed above might be met at the same time, depending on the type of device/procedures and the serious event.
- *Unlikely*: The relationship with the use of the device seems not relevant and/or the event can be reasonably explained by another cause, but additional information may be obtained.
- Possible: The relationship with the use of the investigational device is weak but cannot be ruled out completely. Alternative causes are also possible (e.g. an underlying or concurrent illness/ clinical condition or/and an effect of another device, drug or treatment). Cases were relatedness cannot be assessed or no information has been obtained should also be classified as possible.
- *Probable*: The relationship with the use of the investigational device seems relevant and/or the event cannot reasonably be explained by another cause, but additional information may be

Medtronic Confidential Version: 2.0, 24/Sep/2019 Page 4 of 11

obtained.

- *Causal relationship*: The serious event is associated with the investigational device or with procedures beyond reasonable doubt when:
  - the event is a known side effect of the product category the device belongs to or of similar devices and procedures;
  - the event has a temporal relationship with investigational device use/application or procedures;
  - o the event involves a body-site or organ that
  - o the investigational device or procedures are applied to;
  - o the investigational device or procedures have an effect on;
  - o the serious event follows a known response pattern to the medical device (if the response pattern is previously known);
  - the discontinuation of medical device application (or reduction of the level of activation/exposure) and reintroduction of its use (or increase of the level of activation/exposure), impact on the serious event (when clinically feasible);
  - o other possible causes (e.g. an underlying or concurrent illness/ clinical condition or/and an effect of another device, drug or treatment) have been adequately ruled out;
  - harm to the subject is due to error in use;
  - the event depends on a false result given by the investigational device used for diagnosis, when applicable;
- In order to establish the relatedness, not all the criteria listed above might be met at the same time, depending on the type of device/procedures and the serious event.

Events will be distinguished between the serious adverse events related to the device and those related to the procedures (any procedure specific to the clinical investigation). An adverse event can be related both to procedures and the device. Complications of procedures are considered not related if the said procedures would have been applied to the patients also in the absence of device use/application.

In some particular cases the event may be not adequately assessed because information is insufficient or contradictory and/or the data cannot be verified or supplemented. The sponsor's Medical Monitor and the Investigators will make the maximum effort to define and categorize the event and avoid these situations. Where the Medical Monitor remains uncertain about classifying the serious event, it should not exclude the relatedness and classify the event as "possible".

#### **Adverse Event Outcome Classification**

Outcome of the event will be defined according to the following:

- Fatal: If death was possibly, probably, or causally related to the event
- Not recovered / not resolved: Subject has exited the study and the AE is ongoing and not expected to resolve
- Recovered / resolved: The event has fully resolved prior to study exit
- Recovered / resolved with sequelae: The event has resolved prior to study exit, but retained pathological conditions resulting from the prior disease or injury

Medtronic Confidential Version: 2.0, 24/Sep/2019 Page 5 of 11

- Recovering / resolving: The subject has exited the study and the AE is ongoing but expected to resolve
- Unknown: The subject has exited the study and the AE outcome is unknown

#### **Potential Adverse Events and Definitions**

#### **Atrial Fibrillation**

A disorder characterized by a dysrhythmia without discernible P waves and an irregular ventricular response due to multiple reentry circuits. The rhythm disturbance originates above the ventricles. Degree of severity will be classified according to Common Terminology Criteria for Adverse Events (CTCAE) grade as follows (a semicolon indicates "or" within the description of the grade):

- Grade 1: Asymptomatic, intervention not indicated
- Grade 2: Non-urgent medical intervention indicated
- Grade 3: Symptomatic, urgent intervention indicated; device (e.g., pacemaker); ablation; new onset
- Grade 4: Life-threatening consequences; embolus requiring urgent intervention
- Grade 5: Death

#### **Bronchopleural Fistula**

A disorder characterized by an abnormal communication between a bronchus and the pleural cavity.

Degree of severity will be classified according to Common Terminology Criteria for Adverse Events (CTCAE) grade as follows (a semicolon indicates "or" within the description of the grade):

- Grade 1: Asymptomatic
- Grade 2: Symptomatic, invasive intervention not indicated
- Grade 3: Hospitalization; invasive intervention indicated
- Grade 4: Life-threatening consequences; urgent intervention indicated
- Grade 5: Death

#### **Bronchopulmonary Hemorrhage**

A disorder characterized by bleeding from the bronchial wall and/or lung parenchyma. Degree of severity will be classified according to CTCAE grade as follows (a semicolon indicates "or" within the description of the grade):

- Grade 1: Mild symptoms; intervention not indicated
- Grade 2: Moderate symptoms; medical intervention indicated
- Grade 3: Transfusion, invasive intervention indicated (e.g., hemostasis of bleeding site)
- Grade 4: Life-threatening respiratory or hemodynamic compromise; intubation or urgent intervention indicated
- Grade 5: Death

Medtronic Confidential Version: 2.0, 24/Sep/2019 Page 6 of 11

#### Burn

Unintended microwave burn – unintended tissue ablation

Unintended microwave burn – vessel thrombosis /thrombus /embolism

Unintended microwave burn – diaphragmatic paresis

A finding of impaired integrity to the anatomic site of an adverse thermal reaction. Burns can be caused by exposure to chemicals, direct heat, electricity, flames and radiation. The extent of damage depends on the length and intensity of exposure and time until provision of treatment. Degree of severity will be classified according to CTCAE grade as follows (a semicolon indicates "or" within the description of the grade):

- Grade 1: Minimal symptoms; intervention not indicated
- Grade 2: Medical intervention; minimal debridement indicated
- Grade 3: Moderate to major debridement or reconstruction indicated
- Grade 4: Life-threatening consequences; hemodynamic compromise
- Grade 5: Death

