#### 9.8.5. Safety Endpoints

The primary objective of this prospective, single-arm, multicenter, non-randomized study is to characterize the safety of the Emprint™ Ablation Catheter Kit with Thermosphere™ Technology device in subjects undergoing lung ablation procedures.

The primary endpoint is the composite rate of AEs related to the Emprint™ Ablation Catheter Kit with Thermosphere™ Technology through 1-month follow-up.

In addition, the following secondary safety endpoints will be evaluated:

- Composite rate of SAEs related to the Emprint™ Ablation Catheter Kit with Thermosphere™ Technology through 1-month follow-up.
- Composite rate of all AEs related to the procedure or study devices through 1-month follow-up.
- Composite rate of all SAEs related to the procedure or study devices through 1-month follow-up.

All AEs related to the Emprint™ Ablation Catheter with Thermosphere™ Technology will be graded for severity based on the Common Terminology Criteria for Adverse Events.

MDT18010ILSBA

Version 4.0

26-SEP-2019

Page 28 of 50

For safety reporting, only AEs related to the Emprint™ Ablation Catheter Kit with Thermosphere™ Technology, accessory devices, or study procedures will be captured and reported until the subject exits the study (refer to Section 11.1 for additional details). Related AEs will be summarized as the event counts and percentage which occurred during the ablation procedure or detected after the procedure within the 1-month reporting timeframe. For the primary endpoint, relationship specifically to the Emprint™ Ablation Catheter with Thermosphere™ Technology device will be assessed.

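### The Burn scale in Appendix 17.5 has no Grade 3 criterion for a severe, non-life-threatening vessel thrombosis/embolism or diaphragmatic paresis managed without debridement or reconstruction

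*Protocol*

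**What the plan says.** Protocol 9.8.5 (Safety Endpoints) states that all AEs related to the ablation catheter "will be graded for severity based on the Common Terminology Criteria for Adverse Events". The synopsis, under Safety Assessments, says the same. Appendix 17.5 supplies the grades, term by term.

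The Burn entry of that appendix names three sub-items: unintended tissue ablation, "Unintended microwave burn – vessel thrombosis /thrombus /embolism" and "Unintended microwave burn – diaphragmatic paresis". All three share one scale, and the entry says that a semicolon is to be read as a logical or:

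- "Grade 1: Minimal symptoms; intervention not indicated"
- "Grade 2: Medical intervention; minimal debridement indicated"
- "Grade 3: Moderate to major debridement or reconstruction indicated"
- Grade 4 is life-threatening consequences or hemodynamic compromise, and Grade 5 is death.

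For hemoptysis, hemothorax and lung abscess, among others, the appendix prints the CTCAE general guidelines instead. Their Grade 3 covers severe events that are not immediately life-threatening, and its criteria include hospitalization, disability and limited self-care.

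Protocol 11.2 asks sites to record the diagnosis of an event, where possible, in preference to its symptoms or outcome.

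**The concern.** Thrombosis, embolism and a paretic diaphragm are internal injuries, but the middle of the Burn scale is written in terms of wound care. Its Grade 3 does not mention hospitalization, disability or self-care. An event of one of these types can be severe by the standard that the appendix applies to other lung complications and still fail to meet Grade 3, because nobody would debride or reconstruct anything.

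The primary objective is to characterize the safety of the catheter, and Protocol 10.1.1 lists these microwave injuries among the high-risk residual risks. CTCAE grade is the graded severity measure that the protocol prescribes for catheter-related events; the only other one is the yes/no seriousness flag. A site or medical monitor who follows the appendix exactly could record too low a severity for a catheter injury, and two raters could reasonably grade the same paresis differently.

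**Working it through.** The documents attach no sample-size, power or rate figure to this scale, so there is nothing to reproduce. The check has two steps: place plausible events on both printed scales, then see whether grade enters any analysis.

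**Step 1. Same event, two scales** (semicolon read as or)

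| Event | Burn scale | General guidelines in the same appendix |
|---|---|---|
| Thrombosis or embolism, hospitalized, treated medically, not life-threatening | Grade 2, through medical intervention | Grade 3, through hospitalization |
| Diaphragmatic paresis that is disabling or limits self-care, no intervention indicated | No clear grade: symptoms are not minimal, but the second half of Grade 1 is met and nothing in Grades 2 to 4 applies | Grade 3, through disability or self-care |
| Vessel or diaphragm injury needing surgical repair | Grade 3 is available if repair counts as reconstruction, which is not defined | Grade 3, if severe but not immediately life-threatening |
| Life-threatening consequences | Grade 4 | Grade 4 |
| Death | Grade 5 | Grade 5 |

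The scales part company in the first two rows. The affected band is the event that is severe, not life-threatening, and managed without debridement or reconstruction.

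**Step 2. Where grade is used**

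- Primary endpoint (SAP 7.7.1): the visible rule is a yes/no question on relatedness to the catheter. Grade does not appear.
- Secondary safety endpoints (SAP 7.7.2.1 to 7.7.2.3): relatedness and seriousness questions. Grade does not appear.
- Seriousness (Protocol 11.1.2): serious deterioration that results in hospitalization or permanent impairment qualifies, whatever the grade.
- AE tables (SAP 7.8.2): by system organ class and preferred term. No table by grade is specified.

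A change of grade therefore moves no endpoint rate and no planned table. What changes is the severity recorded for the event. This matters most where the seriousness flag is silent. A disabling paresis that is not judged permanent and leads to neither hospitalization nor intervention meets no listed SAE criterion, so grade is the measure left to show that it was severe.

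**The case against.** The case for leaving the appendix alone has several sound parts.

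- **The top of the scale works.** Grades 4 and 5 do not depend on debridement. A reader might infer that severe catheter injuries in general end up as Grade 1 or 2; the scale does not support that.
- **Grade 3 is narrow but not empty.** The word reconstruction is undefined and may cover surgical repair. The documents do not show that Grade 3 can never be reached for these injuries.
- **Grade 1 for a disabling paresis is a strained reading.** It detaches the no-intervention clause from minimal symptoms, and the general guidelines carry a similar clause at Grade 1. The general guidelines, however, also offer a Grade 3 criterion that such an event meets, and Burn offers none. Saying that the event has no clear grade is the fair description.
- **Intervention-based Grade 3 criteria are common in this list.** Bronchopulmonary hemorrhage, hematoma, pneumonia and ventricular arrhythmia also define Grade 3 by intervention, without hospitalization or self-care. A reader might infer a systematic tilt that grades device injuries below procedural ones; these entries rule that out. They do not close the gap, because their interventions fit the event named, such as transfusion for bleeding or intravenous antibiotics for pneumonia, while debridement does not fit a thrombosed vessel or a paretic diaphragm.
- **The Atrial Fibrillation entry is not a like-for-like comparison.** It puts an embolus requiring urgent intervention at Grade 4. The events at issue here are not life-threatening, and nothing is assumed about urgency.
- **No planned analysis uses grade.** This stands in full and limits the consequence to severity reporting.

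It can also be said that Protocol 11.2 already asks for the diagnosis. That is true, but the appendix names these injuries under Burn, so a site has two instructions that point to different entries.

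**Conclusion.** The point holds in a narrow form. For vessel thrombosis or embolism and for diaphragmatic paresis, the Burn scale has no Grade 3 criterion unless debridement or reconstruction is indicated. A severe, non-life-threatening event outside that condition is recorded as Grade 2 or has no clear grade, where the general guidelines in the same appendix give Grade 3.

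The consequence is limited to the CTCAE severity required by the synopsis and Protocol 9.8.5. The SAE flag and all primary and secondary endpoint rates are unaffected. The number of events affected cannot be computed, because no expected rate is given for these injuries. It is tempting to express the effect as a shift in a Grade 3-or-higher percentage among the up to 30 subjects, but neither document plans such a count.

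The conclusion rests on three assumptions: the semicolon rule is applied as printed; sites grade from Appendix 17.5 and not from some other CTCAE entry; and the parts of the SAP endpoint rules that are not visible contain no grade threshold. The correction is worth making because it is cheap and the protocol asks for grading of exactly these events.

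**What to change.** In Appendix 17.5, take vessel thrombosis/thrombus/embolism and diaphragmatic paresis off the Burn scale. State that each is recorded under its diagnosis, as Protocol 11.2 already asks, with unintended microwave burn given as the cause, and is graded with the CTCAE general guidelines already printed for hemoptysis, hemothorax and lung abscess. The rest of the Burn entry can stay as it is.

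The cost is one wording change and a note to sites and the medical monitor, with no new data and no change to an endpoint rule. There are two small side effects. A few events may carry a higher grade than under the present text; the general Grade 4 also lists urgent intervention as an alternative, which Burn does not. And recording by diagnosis may place an event on a different preferred-term row in the SAP 7.8.2 tables.
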